## **8.5 Planned Interim Analysis, Adaptive Design, and Data Monitoring Committee**

An IA for safety and efficacy will be conducted after 208 subjects complete assessments through the end of treatment (Day 28). Unblinded IA results will be reviewed by the independent DMC for safety evaluation. The interim efficacy analysis will be performed by an unblinded independent statistician.

Analysis at the interim look will be a logistic regression as described for the final analysis. The IA will be restricted to patients who reach Day 28 (or would have reached Day 28 had they not died, withdrawn, or been lost to follow-up). Patients included in the IA will have been randomized at least 28 days prior to IA. It is BioAge's intent that the final and interim analysis do not differ in any important way.

An  $\alpha$  spend is not incorporated into the sample size to account for this look.

Efficacy analyses at IA may yield Conditional Power (CP) results in the Mehta and Pocock promising zone (0.34, 0.90) (Mehta and Pocock, 2011). If so, to maintain the statistical power of the study and to avoid any type 1 error penalty, the Sponsor will consider the option of increasing the sample size (according to the rules provided by Mehta and Pocock), not to exceed N=624 (twice the planned sample size). For this planned IA, Z-score evidence at the IA of between Z=1.41 and 2.21 would define the promising zone and opportunity for BioAge to expand the study. For example, if at IA, Z=1.8 (CP=0.66), then to maintain the power at 0.90 the study could be expanded from 312 subjects to 431. For results in the Mehta and Pocock unfavorable zone, or in the favorable zone, the study will continue to conclusion at N=312 subjects.

The decision to stop the study at IA will be based on a full safety and an early review of efficacy by the Data Monitoring Committee (DMC). To aid the DMC in their recommendation to BioAge regarding conduct of the trial beyond the IA, a table of multiple possible true effects and potential stopping rules will be developed by BioAge and presented in the DMC charter. The operating characteristics of potential decision rules will be shared and understood by the DMC.

## **8.6 Sample Size Calculation and Power Considerations**

Assuming a 31% RF rate in the placebo group and a 15% RF rate in the asapiprant group, for a Fishers Exact test with two-sided 5% Type 1 error and 90% power, the sample size to detect a 16% absolute improvement in the primary endpoint is 312 subjects (1:1 randomization). Randomization will be stratified based on the region within which a subject is enrolled (North America vs. South America) and age (50 to < 75 vs.  $\geq$  75 years of age).

## **8.7 Study Population**

**Enrolled Analysis Set:** all patients who provided informed consent.

**Intent-to-Treat (ITT):** all patients who have been randomized. The ITT will be used for efficacy endpoints. Patients will be analyzed according to the treatment group to which they were randomized. The ITT will be used for the primary efficacy analysis.

**Modified Intent-to-Treat population (mITT):** all ITT patients with exclusion of randomized untreated patients and randomized ineligible patients.

**Per-protocol Set:** all mITT patients with further exclusion of patients with major protocol deviations related to data integrity or eligibility as judged by clinical/biostatistical study personnel prior to database lock. This population will be formed only if > 5% of patients would be excluded.

**Safety Analysis Set:** all patients who have received at least 1 dose of either asapiprant or placebo. The Safety Analysis Set will be used for safety analysis. Patients will be analyzed under actual treatment being received.

**Pharmacokinetic (PK) Set:** all patients who have received at least 1 dose of asapiprant and have at least 1 evaluable post-dose PK concentration value.

**Pharmacodynamic (PD) Set:** all patients who have received at least 1 dose of asapiprant and have at least 1 evaluable post-dose PD value.

### 8.7.1 Pharmacokinetic Analysis

PK parameters will be calculated from plasma asapiprant concentration-time data using noncompartmental methods, and all calculations will be based on actual sampling times. PK parameters will include, but not be limited to, the following:

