a Visit procedures at time of discharge will occur at the date of the dosing visit if visit occurs prior to Day 14, will occur at the Day 14 visit if occurs on Day 14, or will occur on the date of discharge after dosing if after Day 14. This visit is not required if discharge occurs within 2 days after Day 14. If discharge occurs on Day 4, the Day 5 assessments of abbreviated physical exam, safety labs, trough and peak PK, and blood for inflammation markers will not be collected if they were completed as part of the discharge procedures on Day 4.

b Same-day medical record examinations may be used for study purposes to reduce the possible exposure of site staff to COVID-19 risk. Physical examinations may be conducted as standard of care examinations. Abbreviated physical examinations may be conducted by qualified home health care providers or remote/telemedicine visits. Abbreviated physical examinations that cannot be performed at day 5 may be performed up to Day 7.

c WHO Ordinal Scale is derived from subject's oxygen supplementation requirements, hypotension or need for vasopressors, need for renal dialysis, and activity limitations for outpatients.

d Trough PK samples collected within 30 minutes prior to dose.

e ECG and PK sampling to be performed on last day of study treatment if subject remains hospitalized through Day 14. ECG and PK samples are not required on Day 14/EOT if subject is discharged to home before Day 14.

f ECG and PK sampling to be performed at the time of hospital discharge if subject is discharged prior to Day 14. ECG and PK sampling are not required at time of discharge if discharge occurs after the Day 14 visit.

g Peak PK samples collected 3-6 hours after dose.

h Done every other day until 2 qualitative test done at local laboratory is negative. After qualitative test is negative, do viral titer nasopharyngeal testing only on Day 28. For outpatients, scheduled viral titer tests may be skipped on Saturday or Sunday and/or may be skipped if dry ice shipments are not available. In the Saturday or Sunday situation Day 13 tests should be done on the following Monday.

i Safety labs collected within 48 hours prior to consent as part of standard of care can be used to confirm eligibility.

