## 7.2.12 Pharmacokinetic Procedures

The name and address of the bioanalytical laboratory performing the PK assessment for this study will be maintained in the Investigator's files at the/each site and in the Trial Master File at BioAge Labs.

Actual PK blood sample collection times versus time of dosing will be monitored. The time of meal will also be captured, as dosing should occur within 30 minutes of eating. The BioAge Labs expectation is that the Investigator will ensure that every effort is made to collect all PK blood samples at the precise protocol scheduled time. Pre-dose (trough) pharmacokinetic blood collection should be collected within 30 minutes prior to the dose. If subjects are being dosed at home, the subject should be instructed to not dose until the home health visit is conducted. Post-dose (peak) PK blood samples should be collected between 3 and 6 hours after the daily dose. Samples drawn outside these parameters will be considered a protocol deviation.

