**Table 4: Pharmacokinetic Endpoint Summary**

Pharmacokinetic Parameter	Definition
$C_{\max}$	Maximum concentration occurring at $t_{\max}$
$t_{\max}$	Time of maximum observed concentration sampled post-dose
$AUC_{\text{last}}$	Area under the curve from the time of dosing to the last measurable concentration
$t_{1/2}$	Terminal half-life
$\lambda_z$	First-order rate constant associated with the terminal (log-linear) portion of the curve
$CL/F$	Total body clearance for extravascular administration divided by the fraction of dose absorbed
$V_z/F$	Volume of distribution associated with the terminal slope following extravascular administration divided by the fraction of dose absorbed

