### **8.7.1.1 Statistical Analysis of Pharmacokinetic Parameters**

Single samples for PK analysis will be drawn at the time described in [Table 1](#). The times of dosing and sample collection are to be captured. Attempts will be made to develop a PK Population model based on the data. The results of the Population PK analysis will be published in a separate report.

Listing of individual PK concentrations and individual PK parameters of asapiprant will be based on the PK Analysis Sets. Individual concentrations and PK parameters of asapiprant will be listed and summarized by treatment with descriptive statistics (number, arithmetic mean, standard deviation [SD], coefficient of variation [CV%], median, minimum, maximum, geometric mean, and CV% of geometric mean). Figures of individual and mean ( $\pm$  SD) concentration-time profiles of asapiprant by treatments and study parts will be generated based on nominal time points.

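### Protocol Section 8.7.1 commits to noncompartmental half-life, clearance, volume and AUC, but the peak-and-trough sampling in Table 1 does not support them

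*Protocol*

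**What the plan says.** **What will be calculated.** Protocol Section 8.7.1 says that "PK parameters will be calculated from plasma asapiprant concentration-time data using noncompartmental methods", on actual sampling times. Table 4 names seven parameters. AUClast is defined as "Area under the curve from the time of dosing to the last measurable concentration" and lambda-z as "First-order rate constant associated with the terminal (log-linear) portion of the curve"; the others are Cmax, tmax, half-life, CL/F and Vz/F. Section 8.7.1.1 then plans individual listings and a full set of descriptive statistics, without making any of this conditional on the data being adequate.

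**What will be collected.** Section 8.7.1.1 also says "Single samples for PK analysis will be drawn at the time described in" Table 1. The Table 1 footnotes read "Trough PK samples collected within 30 minutes prior to dose" and "Peak PK samples collected 3-6 hours after dose". Section 7.2.12 repeats the second: "Post-dose (peak) PK blood samples should be collected between 3 and 6 hours after the daily dose". Dosing is once daily, and no serial or washout sampling is scheduled.

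**What the trial asks of PK.** The exploratory endpoint (Section 2.3.3) is peak and trough concentration at steady state. The objective (Section 2.2.2) adds a population PK model if one can be built, and Section 8.7.1.1 says this will be attempted and reported separately. The SAP excludes PK analysis (Section 1) and defers it to another plan (Section 12).

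**The concern.** A noncompartmental terminal slope is a regression of log concentration on time through several points known to lie on the declining end of the curve. Half-life and Vz/F follow from that slope. CL/F needs an AUC over a whole dosing interval or to infinity, and Table 4 lists neither. A pre-dose trough and one sample at 3 to 6 hours do not supply these ingredients.

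If Section 8.7.1 is followed literally, the report either has blanks for the terminal-phase parameters or prints values that look like estimates and are not. The second outcome is worse, because a tabulated half-life or volume with a geometric mean and CV% may be reused in later dose or sampling decisions. The PK Set gives no protection: one evaluable post-dose concentration is enough to enter it.

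**Working it through.** **1. Reproduce the protocol's sample count.** Table 1 has peak cells at Day 1, Day 5, Day 14 and discharge (4), and trough cells at Day 5, Day 14 and discharge (3). The early peak is placed on Day 5 because the discharge footnote refers to "the Day 5 assessments of abbreviated physical exam, safety labs, trough and peak PK".

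- 4 + 3 = 7 samples; 7 × 4 mL = 28 mL. This matches the PK row of Table 3.

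**2. Count what one subject can give.** Footnotes e and f make the Day 14 and discharge PK samples alternatives: Day 14 if still in hospital, discharge if that comes before Day 14.

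- Day 1 peak (1) + Day 5 pair (2) + Day 14 or discharge pair (2) = 5.
- With the extra sample after the first nasogastric dose, if any: 5 + 1 = 6.

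**3. Points available for a terminal slope.** After the Day 1 dose there is one scheduled sample, so no slope. On later PK days there is again one post-dose sample. A second point arises only by assuming steady state and reusing the pre-dose trough as the 24-hour value, or when discharge sampling happens to fall on the day after another PK day (for example Day 2 or Day 6). Two points leave 2 − 2 = 0 residual degrees of freedom and no check that the phase is terminal.

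**4. Coverage of AUClast.** From dose to the only post-dose sample: 3/24 = 12.5% to 6/24 = 25% of the interval.

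**5. Illustration.** The documents give no concentrations, so these values are assumed: trough 20, 4-hour value 100, arbitrary units, steady state, 24-hour interval. Every profile below passes exactly through both points. The first two are one-compartment with first-order absorption (rate ka per hour). The others are two-exponential declines from an immediate peak (fast rate a per hour).

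| Profile | True half-life (h) | Cmax | 24 h AUC | Half-life ÷ AUC, relative to row 1 |
|---|---|---|---|---|
| ka 0.3 | 6.4 | 102 | 1480 | 1.0 |
| ka 3.0 | 8.6 | 122 | 1427 | 1.4 |
| a 0.5 | 12 | 350 | 1578 | 1.8 |
| a 0.2 | 48 | 194 | 1363 | 8.1 |
| a 0.5 | 48 | 570 | 1657 | 6.7 |

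- Two-point slope: ln(100/20)/20 = 0.0805 per hour, so half-life = 0.693/0.0805 = 8.6 h for every row, against true values of 6.4 to 48 h.
- Vz/F = (CL/F)/lambda-z, which is proportional to half-life ÷ AUC. It varies about 8-fold (last column).
- CL/F = dose/AUC over the interval. It varies 1657/1363, about 1.2-fold.
- AUClast from the two samples: (20 + 100)/2 × 4 = 240. As a share of the true 24-hour AUC: 240/1657 = 14% to 240/1363 = 18%.
- If the trough is reused at 24 h, the linear trapezoid gives 240 + (100 + 20)/2 × 20 = 1440, inside the true range of 1363 to 1657.

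**6. Cmax and tmax.** Both are whatever the single draw returns. In the illustration that is 100 at 4 h, whatever the true peak.

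**The case against.** **The operative PK plan is a separate document.** This is the strongest point. The SAP defers PK to a plan that was not supplied, and that plan may already drop the unsupported parameters. A reader might infer that the trial will report meaningless PK values; the documents do not show that. They show that Protocol Section 8.7.1 does not fit Protocol Table 1.

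**The population model covers it.** In part. Sparse sampling suits such a model, but the protocol only undertakes to attempt one, and it stands beside the noncompartmental commitment without replacing it. Nor do the documents show that troughs and 3-to-6-hour samples would identify V/F.

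**No stated endpoint depends on the contested rows.** True. The mentions of study parts (Section 8.7.1.1) and of part and cohort digits in the PK label (Section 7.2.12.1) do not fit this design and suggest carried-over text. That is inference. It would explain the mismatch without removing it.

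**Not all of Table 4 is unobtainable.** Correct. A reader might conclude that AUClast, half-life, lambda-z, CL/F and Vz/F are all equally impossible. That goes too far: AUClast is computable as defined, and CL/F is usable to the extent that steady state and the reused trough are accepted.

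**Two counting points.** The 7 in Table 3 might be read as samples per subject; footnotes e and f rule that out. It is also not strictly true that an interval never holds more than one trough and one peak. The nasogastric sample may fall on a PK day, and discharge on Day 6 after Day 5 sampling gives a trough at each end of an interval. Neither guarantees a usable terminal phase.

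**Conclusion.** The point holds as an inconsistency within the protocol. Under the Table 1 schedule:

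- **Lambda-z, half-life and Vz/F:** not reliably estimable by noncompartmental methods.
- **AUClast:** calculable, but it describes only the first 3 to 6 of 24 hours.
- **CL/F:** depends on assuming steady state and reusing the trough as the 24-hour value.
- **Cmax and tmax:** set by the single draw.

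The sample count and the coverage come directly from the protocol. The size of the errors in step 5 rests on assumed concentrations and curve shapes. The one-compartment rows alone span half-lives of only 6.4 to 8.6 h; the wider spread comes from the two-exponential shapes, which the data could not rule out.

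The consequence is small. PK is exploratory, and the primary analysis, sample size and interim rule do not use it. Whether the separate PK plan already resolves the point cannot be judged from the documents.

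**What to change.** In Protocol Section 8.7.1 and Table 4, and in the separate PK analysis plan if it does not already say so:

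1. Limit noncompartmental output to observed peak and trough concentrations by day, in line with the stated PK endpoint, with actual sampling times listed.
2. Report AUC, CL/F, V/F and half-life only from the population PK model, and only if the model is successfully developed and the sparse data identify them. Otherwise do not report them.

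The cost is wording; no extra samples are needed. The SAP addendum says that enrollment has stopped and all enrolled patients have passed Day 28, so added sampling is not an option in this trial. The practical places for the change are the PK analysis plan and the study report.

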**Table 4: Pharmacokinetic Endpoint Summary**

Pharmacokinetic Parameter	Definition
$C_{\max}$	Maximum concentration occurring at $t_{\max}$
$t_{\max}$	Time of maximum observed concentration sampled post-dose
$AUC_{\text{last}}$	Area under the curve from the time of dosing to the last measurable concentration
$t_{1/2}$	Terminal half-life
$\lambda_z$	First-order rate constant associated with the terminal (log-linear) portion of the curve
$CL/F$	Total body clearance for extravascular administration divided by the fraction of dose absorbed
$V_z/F$	Volume of distribution associated with the terminal slope following extravascular administration divided by the fraction of dose absorbed

### **8.7.1.1 Statistical Analysis of Pharmacokinetic Parameters**

Single samples for PK analysis will be drawn at the time described in [Table 1](#). The times of dosing and sample collection are to be captured. Attempts will be made to develop a PK Population model based on the data. The results of the Population PK analysis will be published in a separate report.

Listing of individual PK concentrations and individual PK parameters of asapiprant will be based on the PK Analysis Sets. Individual concentrations and PK parameters of asapiprant will be listed and summarized by treatment with descriptive statistics (number, arithmetic mean, standard deviation [SD], coefficient of variation [CV%], median, minimum, maximum, geometric mean, and CV% of geometric mean). Figures of individual and mean ( $\pm$  SD) concentration-time profiles of asapiprant by treatments and study parts will be generated based on nominal time points.

### **8.7.2 Pharmacodynamic Analysis**

Exploratory inflammation markers are planned for this study. Pharmacodynamic samples may be maintained for up to 5 years after the clinical study report has been finalized.

Remaining aliquots of blood or tissue samples from any of the scheduled time points may also be analyzed for additional exploratory inflammation markers or PK-related activities (i.e., validation of a new bioanalytical method). This exploratory research is intended to aid the further understanding of asapiprant provided it does not add to the blood volume presented in [Table 3](#).

Any results from this additional exploratory research will be reported separately from the main clinical study report. The results may be used internally to help support the design of further clinical studies, form part of scientific publication, or be made known to the regulatory authorities as part of a new drug application. The Sponsor has no obligation to perform this additional exploratory research.

### **8.7.2.1 Statistical Analysis of Pharmacodynamic Parameters**

## **8.8 Safety Analyses**

Safety endpoint:

1. Incidence and severity of treatment-emergent AEs (TEAEs)
2. Safety outcome measure:
  - a) Occurrence of AEs
  - b) Laboratory safety parameters such as complete blood count, blood glucose, electrolyte, hepatic and renal functions taken before the first dose and on Days 2, 5, 14, 28 and at the time of discharge to find any changes or any systemic effect after treatment

Adverse events will be coded using the Medical Dictionary for Regulatory Activities (MedDRA) Version 23.1. The number of events, incidence, and percentage of TEAEs will be calculated overall, by system organ class, by preferred term, and by treatment group for each cohort and treatment group. The number and percentage of subjects with TEAEs will be further summarized

by severity and relationship to IP. Adverse events related to IP, AEs leading to withdrawal, SAEs, and deaths will be similarly summarized/listed.

Clinical laboratory tests, vital signs, and ECG findings will be summarized by treatment group and visit for the study. Descriptive statistics will be calculated for quantitative safety data as well as for the difference from baseline, if applicable. Frequency counts will be compiled for classification of qualitative safety data. Baseline for safety data will be defined as the last value prior to dose. Potentially clinically important findings will also be summarized or listed.

## **8.9 Other Analyses**

No other analyses are planned in this study.

## **10 APPENDICES**

## **APPENDIX 1**

## PROTOCOL HISTORY

Document	Date	Global/Country/Site Specific
Version 5.0, Amendment 04	07 September 2021	Global
Version 4.0, Amendment 03	19 May 2021	Global
Version 3.0, Amendment 02	26 April 2021	Global
Version 2.0 (Amendment 01)	19 March 2021	Global
Original Protocol (V1.0)	04 Dec 2020	Global

## **APPENDIX 2**

## **1 REGULATORY, ETHICAL, AND STUDY OVERSIGHT CONSIDERATIONS**

## **REGULATORY AND ETHICAL CONSIDERATIONS**

This study is conducted in accordance with current applicable regulations including ICH E6(R2), EU Directive 2001/20/EC, and all updates, as well as local ethical and legal requirements.

Compliance with these regulations and guidelines also constitutes compliance with the ethical principles described in the Declaration of Helsinki.

The name and address of each third-party vendor (e.g., CRO) used in this study will be maintained in the Investigator's and Sponsor's files, as appropriate.

## **2 SPONSOR'S RESPONSIBILITIES**

### **Good Clinical Practice Compliance**

The study Sponsor and any third party to whom aspects of the study management or monitoring have been delegated will undertake their assigned roles for this study in compliance with all applicable industry regulations, current ICH GCP guideline E6 (1996 [R2, 2016]), EU Directive 2001/20/EC Guidelines, as well as all applicable national and local laws and regulations.

Visits to sites are conducted by representatives of the study Sponsor and/or the company organizing/managing the research on behalf of the Sponsor to inspect study data, subjects' medical records, and CRFs in accordance with current GCP and the respective local and (inter)national government regulations and guidelines. Records and data may additionally be reviewed by auditors or by regulatory authorities.

The Sponsor (or a nominated designee) ensures that local regulatory authority requirements are met before the start of the study. The Sponsor (or a nominated designee) is responsible for the preparation, submission, and confirmation of receipt of any regulatory authority approvals required prior to release of investigational product for shipment to the site.

